8.4 Analytic Plan

8.4.1 Analytic Plan for Primary Endpoints

Part A:

The recommended phase 2 dose and schedule of ^{177}Lu -PSMA-617 will be determined from the aggregate of the safety and efficacy data observed.

Part B:

Objective response is defined as the best response (complete response or partial response) defined by RECIST v1.1, from the start of treatment until disease progression or recurrence, where the reference for progressive disease is the smallest measurements recorded from start of treatment. To be assigned a status of objective response (CR or PR), changes in tumor measurements must be confirmed by repeat scans no less than 4 weeks after the criteria for

response are first met. The proportion of patients with objective response will be descriptively reported with 95% confidence interval.

8.4.2 Analytic Plan for Secondary Endpoints

Median duration of response

Median duration of response will be estimated using Kaplan-Meier product limit method, starting with the date of first scan indicating response until loss of response or progression, or death, whichever occurs first.

PSA response rate

The proportion of patients who achieve a greater than 50% decline from baseline PSA drawn on C1D1, at any point in the treatment course, will be descriptively reported along with 95% confidence interval.

PSA progression free survival

PSA progression will be defined using PCWG3 criteria. Median PSA progression free survival will be estimated using the Kaplan-Meier method. Duration will be measured from date of first treatment to date of first PSA meeting criteria for PSA progression.

Time to symptomatic skeletal related event

Symptomatic skeletal related event is defined as the first occurrence of one or more of the following: symptomatic fracture, surgery or radiation to bone, or spinal cord compression. The median time to symptomatic skeletal related event will be determined using Kaplan-Meier method.

Safety

The incidence and severity of adverse events related to study treatment will be descriptively reported using CTCAE v4.0.

Radiographic progression free survival and 6-month rPFS rate:

Radiographic progression of disease will be defined by RECIST v1.1 and PCWG3 criteria. For the first scheduled reassessment by bone scan (at Cycle 2), new bone lesions will require a confirmatory bone scan 6 or more weeks later. Median PFS will be estimated using the Kaplan-Meier method. Durations will be measured from the first day of study treatment (Cycle 1) to the first date of radiographic progression or death, whichever occurs first. Patients who discontinue study treatment for toxicity, withdraw from the study, or have PSA-only progression will be censored at the date of the last radiographic tumor assessment. Patients who discontinue treatment for clinical progression or deterioration will be included in the analysis.

Overall survival

Median overall survival and 95% confidence interval will be estimated using the Kaplan-Meier method. Duration will be measured from first date of study therapy to date of death from any cause.

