2.1 Objectives

Primary Objectives

Part A: To determine the recommended phase 2 dose and schedule of ¹⁷⁷Lu-PSMA-617 in combination with pembrolizumab in patients with mCRPC.

Part B (Dose Expansion): To determine the objective response rate by RECIST 1.1 criteria.

Secondary Objectives

1. To characterize the safety profile of the combination.
2. To determine the median duration of response by RECIST 1.1 criteria.
3. To determine the proportion of patients who experience $\geq 50\%$ decline from baseline in serum PSA.
4. To determine the median PSA progression-free survival.
5. To determine the median time to symptomatic skeletal related event.
6. To determine the 6 month radiographic progression-free survival rate and median radiographic progression-free survival.
7. To determine the median overall survival.

Correlative Objectives

1. To assess the lesion-specific response rate by baseline PSMA avidity on ⁶⁸Ga-PSMA-11 PET.
2. To quantify the change from baseline in T cell repertoire, circulating T cell subsets, tumor infiltrating lymphocytes, and tumor PD-L1 expression by immunohistochemistry after one priming dose of Lu-PSMA RLT.
3. To explore the relationship between timing of the ¹⁷⁷Lu-PSMA-617 priming dose with initiation of pembrolizumab with respect to immunologic, safety, and efficacy outcomes.
4. To descriptively characterize the patterns of uptake on ⁶⁸Ga-PSMA-11 PET at the time of disease progression.
5. To explore relationship between tumor genomic profile with clinical outcomes including response rate and progression-free survival.
6. To explore the relationship between tumor dosimetry with objective response.

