2.2.2 Secondary Endpoints

1. Frequency and severity of adverse events as defined by CTCAE criteria.
2. Median duration of response by RECIST 1.1
3. PSA response rate
4. Radiographic progression-free survival rate at 6 months and median radiographic progression-free survival.
5. Overall survival

3 Study Design

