3.1 Characteristics

This is a single-center Phase 1b open-label, study of PSMA-targeted radionuclide therapy with ¹⁷⁷Lu-PSMA-617 in combination with pembrolizumab in patients with mCRPC who have previously progressed on at least one prior androgen pathway inhibitor (e.g. abiraterone, enzalutamide, apalutamide). Patients must have at least three metastatic lesions which are PSMA-avid on baseline ⁶⁸Ga-PSMA-11 PET imaging.

In **Part A** of the study, patients will be enrolled in sequential fashion to one of treatment schedules with respect to timing of ¹⁷⁷Lu-PSMA-617 in relation to first dose of pembrolizumab (N = 6 evaluable patients per schedule):

Schedule 1) Priming dose of ¹⁷⁷Lu-PSMA-617 administered on Cycle 1 Day 1 followed by pembrolizumab 200 mg IV q 21 days starting Cycle 2 Day 1.

Schedule 2) Priming dose of ¹⁷⁷Lu-PSMA-617 administered concurrently with initiation of pembrolizumab on Cycle 1 Day 1.

Schedule 3) Priming dose of ¹⁷⁷Lu-PSMA-617 administered on Cycle 1 Day 1 following initiation of pembrolizumab on Cycle 1 Day -21.

The priming dose of ¹⁷⁷Lu-PSMA-617 will be 7.4 +/- 15% GBq, which is the recommended phase 3 dose of the agent. If the DLT frequency exceeds 33% including patients across the three schedules, Dose Level -1 of ¹⁷⁷Lu-PSMA-617 will be investigated (4 Gbq +/- 15%).

6 evaluable patients will be enrolled in each of the three cohorts in sequential fashion in Part A of the study. The DLT window will be Cycle 1 + Cycle 2. If the DLT frequency is \geq 33% for a

particular cohort, that dosing schedule will be determined to be non-tolerable and the next schedule will be evaluated. In addition, if the DLT frequency attributable specifically to Lu-PSMA-617 is $\geq 33\%$ after 6 or more evaluable patients are enrolled in Part A of the study, the dose of Lu-PSMA-617 will be reduced to Dose Level -1 (4 GBq +/- 15%) for the remainder of patients enrolled on study. If the DLT frequency attributable to Lu-PSMA-617 at Dose Level -1 is $\geq 33\%$ after 6 or more patients are treated at Dose Level -1, study accrual will be halted.

Using the data obtained in Part A, the recommended phase 2 dose and schedule of ^{177}Lu -PSMA-617 will be determined by the DSMC and Principal Investigator using a combination of safety, efficacy, and immunologic effects of treatment from the first two cycles (and additional cycles of treatment when available).

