7.7 Post-treatment PSA Changes

All patients will be evaluated for PSA decline. Patients with disease that is not measurable will be eligible for this study and will be assessed for response based on changes in PSA and serial bone scans (if appropriate). The baseline serum PSA must be at least 2 ng/mL. Patients who show PSA increases will not be evaluated for PSA progression prior to 12 weeks of study therapy.

- a. 30% and 50% PSA Decline: PSA decline of at least 30% and 50%, respectively, from baseline confirmed by a second measurement at least 3 weeks later. The reference for these declines should be a PSA measured within 2 weeks prior to starting therapy.
- b. PSA Progression: Prostate Cancer Working Group 2 (PCWG2) Criteria will be reported. PSA progression occurs when the PSA has increased 25% or greater above nadir and an absolute increase of 2 ng/mL or more from the nadir is documented. Where no decline is observed, PSA progression similarly occurs when a 25% increase from baseline value along with an increase in absolute value of 2 ng/mL or more. Patients will receive a minimum of 12 weeks of therapy prior to being evaluable for this endpoint. PSA progression (without evidence of progression on scans) will not be criteria for discontinuation of study therapy.
- c. PSA Response Duration: The PSA response duration commences on the date of the first 50% decline in PSA. The response duration ends when the PSA value increases by 25% above the nadir, provided that the increase in the absolute-value PSA level is at least 5 ng/mL or back to baseline, whichever is lower.
- d. Progressive Disease by PSA (as defined by PSA Progression, above)
- e. Time to PSA Progression: The start of the time to PSA progression is the day treatment is initiated. The end date is the date of the first PSA rise over the determined PSA PD value.

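### Sections 7.7 and 8.4.2 define PSA50 response differently: only 7.7 requires confirmation, their baselines conflict in Schedule 3, and neither is said to govern

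*Combined protocol and SAP*

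**What the plan says.** Four places in the combined protocol and SAP bear on this endpoint.

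- Section 2.1 sets a secondary objective on the share of patients whose PSA falls by 50% or more. It does not mention confirmation.
- Section 2.2.2 lists the endpoint only by its label, "PSA response rate".
- Section 7.7, item a, gives a measurement rule: "PSA decline of at least 30% and 50%, respectively, from baseline confirmed by a second measurement at least 3 weeks later". It also fixes the baseline: "The reference for these declines should be a PSA measured within 2 weeks prior to starting therapy". The same section sets a minimum baseline PSA of 2 ng/mL.
- Section 8.4.2 gives the analysis rule. It counts patients "who achieve a greater than 50% decline from baseline PSA drawn on C1D1, at any point in the treatment course". It has no confirmation step and does not refer back to Section 7.7.

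The timing of C1D1 also matters. In Schedule 3, according to Section 3.1, the radioligand is given on C1D1 "following initiation of pembrolizumab on Cycle 1 Day -21". The Section 5.4 calendar agrees and shows PSA draws at screening, on Day -21 and on C1D1.

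**The concern.** Both sections are current and operative, and two analysts following them could classify the same patient differently. They differ in the threshold (at least 50% against more than 50%), in confirmation and in the baseline sample.

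Confirmation matters most. If any qualifying value in a long series of PSA draws counts, one low reading makes a responder. Under Section 7.7a that reading must hold up at least 3 weeks later. The baseline matters in Schedule 3, where a C1D1 value already reflects about three weeks of pembrolizumab.

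At stake is the meaning of the reported PSA50 rate and its use in the exploratory Fisher tests of Section 8.4.3. The rate may also contribute to the efficacy evidence which, under Sections 3.1 and 8.4.1, helps choose the Part B dose and schedule. A baseline that is pre-treatment in two schedules and on-treatment in the third would blur a comparison of schedules on PSA response.

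**Working it through.** The documents give no target, power or expected value for PSA response in this trial, so there is no planned figure to reproduce. The check compares the definitions and then illustrates their effect.

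1. **Threshold.** The two rules differ only for a decline of exactly 50%. This is negligible in practice, and on this element alone Section 8.4.2 is marginally the stricter.

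2. **Confirmation.** Take one baseline and one observation period, and set exact ties aside. Every patient who meets Section 7.7a has at least one decline above 50%, so also meets Section 8.4.2. The reverse need not hold. Hence rate(7.7a) ≤ rate(8.4.2).

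3. **Baseline, Schedules 1 and 2.** C1D1 is the first treatment day. A C1D1 sample taken before dosing also lies within the two weeks before therapy, so one sample can satisfy both sections.

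4. **Baseline, Schedule 3.** Let P₀ be the pre-dose PSA on Day -21 and P₁ the PSA on C1D1, 21 days after the first pembrolizumab dose. If therapy starts with the first study drug, P₁ cannot be the Section 7.7a reference. A responder must reach 0.5 × P₀ under Section 7.7a but 0.5 × P₁ under Section 8.4.2. If PSA rose in between (P₁ > P₀), Section 8.4.2 is easier to meet; if it fell, harder. The documents do not say which to expect. The number affected is 6 of the 18 planned Part A patients, or 6 + 25 = 31 of 43 overall if Schedule 3 goes forward to Part B.

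5. **Size of the confirmation effect.** The unconfirmed share u is an assumption. Confirmed rate = any-time rate × (1 − u).
   - u = 0.10: 50% × 0.90 = 45%, a loss of 0.05 × 25 = 1.25 patients.
   - u = 0.20: 50% × 0.80 = 40%, a loss of 0.10 × 25 = 2.5 patients.

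   In whole patients, with exact (Clopper-Pearson) 95% intervals and N = 25:

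   | Unconfirmed | Responders | Rate | 95% CI |
   |---|---|---|---|
   | 0 of 12 | 12/25 | 48% | 27.8–68.7% |
   | 1 of 12 (about 10%) | 11/25 | 44% | 24.4–65.1% |
   | 2 of 12 (about 20%) | 10/25 | 40% | 21.1–61.3% |
   | 4 of 12 (about 30%) | 8/25 | 32% | 14.9–53.5% |

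   For any-time rates of 40% to 60% and u from 10% to 30%, the gap at N = 25 runs from 4 points (10 to 9 patients) to 16 points (15 to 11 patients).

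6. **Can the existing draws confirm?** PSA is drawn on Day 1 of 21-day cycles, with visits allowed ±3 days. Consecutive draws can therefore be as close as 21 − 6 = 15 days, short of 3 weeks. Draws two cycles apart are at least 42 − 6 = 36 days apart, or 33 if labs are also taken up to 3 days before a dose. A later scheduled draw can therefore always meet the interval, but the next one may not.

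**The case against.** The best defence is that the sections divide the work: Section 7 says how response is measured, and Section 8.4.2 names the summary statistic. On that view the confirmation rule carries over, and the wording in 8.4.2 only says when a decline may occur. Section 8.4.2 nowhere says that one unconfirmed value is enough. A reader might infer that it deliberately rejects confirmation, but the text is silent rather than contrary. The defence still does not settle the matter. Section 8.4.1 writes out confirmation for objective response although Section 7.4 already has it, so silence on PSA can fairly be read as leaving it out.

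A reader might also infer that the baselines clash throughout the trial, or that the C1D1 baseline inflates the Schedule 3 rate. The documents support neither: in Schedules 1 and 2 one sample can serve both rules, and the Schedule 3 effect has no known direction. If the Section 7.7a reference to starting therapy meant the radioligand, even the Schedule 3 clash would disappear, but the text does not say so.

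On size, a shift of 1 to 3 patients is small beside the interval for 12/25. It is tempting to call the shift material against the 40–60% range in the abstract's rationale. However, that range covers both PSA and objective response in other studies, the plan tests nothing against it, and a fall from 50% to 45–40% stays inside it. This objection to the size stands.

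**Conclusion.** The plan is wrong as written: one endpoint has two definitions and no rule of precedence. Two consequences are established. Section 8.4.2 can only give an equal or higher PSA50 rate through the missing confirmation, with the baseline held fixed and exact ties set aside. In Schedule 3 it uses an on-treatment baseline, provided that therapy is taken to start with the first study drug.

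The illustrative loss of 5 to 10 percentage points from a 50% rate rests wholly on the assumed 10–20% unconfirmed share. The true share could be smaller or larger.

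Nothing here reaches the primary objective response rate, the sample size or any numerical decision rule. PSA50 is descriptive apart from its exploratory use in Section 8.4.3. The point should be corrected before analysis, but it does not threaten the trial's main conclusion.

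**What to change.** Replace the Section 8.4.2 definition with:

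> PSA response is a decline of at least 50% from the last PSA before the first dose of any study drug (within 2 weeks before that dose; in Schedule 3, the Day -21 pre-dose sample), confirmed by a second PSA at least 3 weeks later, which may be any later scheduled draw if the next one falls under 3 weeks (Section 7.7).

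Also:

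- Apply the Section 7.7 minimum baseline PSA of 2 ng/mL to the denominator and report how many patients it removes. Section 3.5 otherwise has everyone who received the priming dose analysed.
- Say whether a draw after the end of treatment may serve as confirmation.
- Report the best unconfirmed decline at any time as a separately named descriptive figure.

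If the sponsor prefers the any-time definition as the main one, Section 7.7a must change instead. The essential step is to fix one definition before the data are analysed.

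The cost is a short text amendment. PSA is already drawn at screening, on Day -21 in Schedule 3 and on Day 1 of each cycle, so no visit or sample is added. The downside is that the headline rate may be slightly lower.

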Number of patients	
Approximately 18 patients will be enrolled during Part A of the study. An additional 25 patients will be enrolled in Part B.
 
Total sample size: 43
 
Part A: N ~ 18 patients (6 patients per Schedule; 3 Schedules to be evaluated)
 
Part B: N ~ 25 patients

Duration of Therapy	Patients will be treated until disease progression per PCWG3/RECIST 1.1 criteria, confirmed by repeat scans performed \geq 4 weeks later, unacceptable toxicity, or patient withdrawal, whichever occurs first.
Duration of Follow up	Patients will undergo safety follow up visit approximately 30 days and 90 days following end of treatment visit.
Duration of study	The study is anticipated to accrue 2-3 patients per month for an estimated accrual period of 21 months. The study is expected to reach completion for analysis of primary and secondary endpoints approximately 36 months from first patient enrolled.
Study Drugs	
¹⁷⁷Lu-PSMA-617 is a PSMA-targeted radioligand that will be produced under Current Good Manufacturing Practice (CGMP) regulations. The priming dose of ¹⁷⁷Lu-PSMA-617 will be 7.4 +/- 15% GBq, which is the recommended phase 3 dose of the agent.
 
The planned dose schedules to be evaluated in Part A of the study include:
 
Schedule 1) Priming dose of ¹⁷⁷Lu-PSMA-617 administered on Cycle 1 Day 1 followed by pembrolizumab 200 mg IV q 21 days starting Cycle 2 Day 1.
 
Schedule 2) Priming dose of ¹⁷⁷Lu-PSMA-617 administered concurrently with initiation of pembrolizumab on Cycle 1 Day 1.
 
Schedule 3) ¹⁷⁷Lu-PSMA-617 administered on Cycle 1 Day 1 following initiation of pembrolizumab on Cycle 1 Day -21.
 
The cumulative safety data, including safety data beyond Cycle 2 where available, immunologic priming effects, along with efficacy and pharmacodynamic data, will be utilized to determine the recommended schedule of ¹⁷⁷Lu-PSMA-617 in combination with pembrolizumab.

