Despite the significant anti-tumor activity with Lu-PSMA RLT, there are several significant limitations of this approach as monotherapy: 1) There is significant **heterogeneity of PSMA expression**, both in analysis of individual circulating tumor cells as well as diagnostic PSMA PET imaging of metastatic lesions across individual patients, and 2) Within PSMA-avid lesions, there is a **limited duration of response**. In a recently presented prospective phase 2 study of Lu-PSMA, despite enriching for patients with more homogenous level of PSMA uptake on baseline PET imaging, the median PSA progression-free survival by PCWG criteria was only 6.3 months (95% CI 4.8 – 8.3), and median overall survival only 12.7 months. Nearly half of the 30 patients enrolled received less than the pre-specified 4 doses of Lu-PSMA treatment, for both toxicity-related reasons (hematologic, salivary gland) as well as rapid disease progression following initial response. The reasons for rapid disease progression include baseline heterogeneity of PSMA expression among disseminated tumor cells, leading to diffuse bone marrow involvement in a subset of patients. There is a clear and unmet medical need to merge the rapid anti-tumor responses achieved by Lu-PSMA RLT with a treatment that can both sustain and spread response to PSMA-negative lesions without excess cumulative toxicity.

Immune checkpoint inhibition, by virtue of antigen spread induced by immunogenic cell death induced by antecedent radioligand treatment, may accomplish this goal.

1.4 Immune Checkpoint Inhibition Leads to Durable Responses in a Minority of mCRPC Patients

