8.2 Accrual

The estimated accrual period is 21 months, and total study duration (first patient enrolled to last patient off study) is 36 months.

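### The Kaplan-Meier median for time to symptomatic skeletal event censors deaths, so it can be reported when fewer than half of patients would ever have an event

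*Combined protocol and SAP*

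**What the plan says.** Section 2.1 lists as a secondary objective: "To determine the median time to symptomatic skeletal related event". Section 8.4.2 defines the event as the "first occurrence of one or more of the following: symptomatic fracture, surgery or radiation to bone, or spinal cord compression", and then states: "The median time to symptomatic skeletal related event will be determined using Kaplan-Meier method". Death is not in the definition. For this endpoint the section gives no time origin, no censoring rule and no competing-risk method.

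Other endpoints in the same section treat death differently. Duration of response runs "until loss of response or progression, or death, whichever occurs first", and radiographic progression-free survival runs to the "first date of radiographic progression or death, whichever occurs first".

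The only overall survival figure in the documents is in the Section 1.3 account of an earlier single-agent Lu-PSMA study: "median overall survival only 12.7 months". On timing, Section 8.2 says: "The estimated accrual period is 21 months, and total study duration (first patient enrolled to last patient off study) is 36 months". The abstract gives "Total sample size: 43", of whom 25 are in Part B. The abstract and the three study calendars schedule visits only to 90 days after treatment.

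**The concern.** The plan does not say in words that deaths are censored. It follows from the method: where death is not an event, Kaplan-Meier can only censor a patient who dies without a skeletal event, at death or before. Censoring treats that patient as someone who could still have the event later, which is not possible. Death is therefore a competing event.

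One minus Kaplan-Meier estimates the risk in a setting where nobody dies first. It always falls to 50% if the skeletal hazard continues, whatever share of patients is really affected. A reader will take a reported median to mean that half of the patients had a skeletal event by that time. In a population with substantial mortality this may be far from true, and half may never have one. At stake is how a stated secondary objective is read.

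**Working it through.** The documents give no figure for this endpoint, so there is none to reproduce. The check asks what a given Kaplan-Meier median means for patients.

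**Inputs**
- Median time to death, M_d: 12.7 months (Section 1.3, borrowed from the earlier study). Sensitivity value: 20 months (assumption).
- Kaplan-Meier (cause-specific) median time to skeletal event, M_s: not in the documents, so varied.
- Independent exponential times (assumption), with h_s = ln2/M_s and h_d = ln2/M_d.

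**Formulas**
- Kaplan-Meier with deaths censored targets 1 − exp(−h_s·t).
- Cumulative incidence: h_s/(h_s + h_d) × [1 − exp(−(h_s + h_d)·t)].
- Share ever affected: h_s/(h_s + h_d) = M_d/(M_s + M_d). This is below one half whenever M_s exceeds M_d.

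**Example 1: M_s = 18, M_d = 12.7.** h_s = 0.0385, h_d = 0.0546, sum 0.0931.
- Ever affected: 12.7/30.7 = 41%.
- By 18 months, where Kaplan-Meier reads 50%: 0.414 × [1 − exp(−1.676)] = 0.414 × 0.813 = 34%.

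| Month | 1 − Kaplan-Meier | Cumulative incidence |
|---|---|---|
| 6 | 20.6% | 17.7% |
| 12 | 37% | 28% |
| 18 | 50% | 34% |
| 24 | 60% | 37% |

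**Example 2: M_s = 24, M_d = 20.** h_s = 0.0289, h_d = 0.0347, sum 0.0635.
- Ever affected: 20/44 = 45%.
- By 24 months: 0.455 × [1 − exp(−1.525)] = 0.455 × 0.782 = 36%.

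**A case where the problem recedes: M_s = 18, M_d = 20.** Ever affected: 20/38 = 53%, so a majority eventually has an event.

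**Could such a median be reported in this trial?** Simulation of 4,000 trials per setting, with uniform accrual over 21 months, data cut at 36 months and skeletal follow-up to death or data cut. The table gives the share of trials that report a Kaplan-Meier median while fewer than half of the patients had an observed event.

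| M_d | Ever affected | M_s | N = 25 | N = 43 |
|---|---|---|---|---|
| 12.7 | 30% | 29.6 | 44% | 48% |
| 12.7 | 40% | 19.0 | 69% | 83% |
| 20 | 40% | 30.0 | 46% | 53% |

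These shares also include administrative censoring at 36 months, which by itself can give a median with fewer than half observed events. They show that the situation can arise in a trial of this size, not how much of it is due to deaths.

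**The case against.** **Net or crude risk is a choice of estimand.** Under independence, Kaplan-Meier does estimate the cause-specific median consistently. That is true, but the plan does not say that it wants the hypothetical quantity, and a bare median will be read as describing patients.

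**The size is borrowed.** The 12.7 months comes from a study of repeated single-agent dosing. This trial adds pembrolizumab, requires ECOG 0 or 1 and excludes taxane use in the castration-resistant setting (Section 3.3), so survival may be longer. The figure is also all-cause survival, used here as the hazard of death before a skeletal event. This stands: the numbers are illustrations.

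**Follow-up may be short.** If skeletal events are collected only to about 90 days after treatment, many deaths fall after patients are already censored, and the bias shrinks. This stands. Censoring when contact ends, often around progression, may itself be informative, and a competing-risk method does not remove that.

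**Precision is low.** In Example 1 the 6-month gap is 2.9 points. The 95% half-width is about 1.96 × √(0.177 × 0.823/25) = 15 points at N = 25 and 11 points at N = 43 (normal approximation, no censoring). This stands for early times; the gap is 16 points by 18 months.

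**Stakes are low.** The endpoint is descriptive and is missing from the Section 2.2.2 list of secondary endpoints, though it is an objective in Section 2.1. This stands.

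Three stronger readings are tempting but not supported:
- A reader might infer that the reported median would look better or worse depending on survival. Under independence, 1 − exp(−h_s·t) contains no death hazard. It is the cumulative incidence that moves with survival.
- A reader might infer that the median is too short. In Examples 1 and 2 no cumulative-incidence median exists for it to be shorter than.
- A reader might infer that the trial will publish inflated event rates. Section 8.4.2 plans only a median here; the percentages above show what that median means and are not planned outputs.

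**Conclusion.** The point holds. As written, deaths without a skeletal event are censored, and the resulting median refers to a setting without death. It can be reported when fewer than half of patients would ever be affected: about 34% by then and 41% ever in Example 1, 36% and 45% in Example 2.

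These figures rest on independent exponential times, a death rate from another study or an assumed one, and a skeletal event rate that the documents do not give. Under those assumptions the share of patients affected by the Kaplan-Meier median is below 50%; how far below is uncertain, and the gap is small at 6 months or with short skeletal follow-up. It would be too much to infer that a trial result is invalidated: the endpoint is secondary, descriptive and single-arm, and no test, sample size or decision rule depends on it. It is still worth changing, because a better-suited standard estimator is available at little cost.

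**What to change.** In Section 8.4.2:
1. Estimate the cumulative incidence of first symptomatic skeletal event with death before it as a competing event (Aalen-Johansen), measured from first study treatment. Give 95% CIs at 6 and 12 months, and a median only if the curve reaches 50%.
2. Censor both event types at the last date on which skeletal events were ascertained. Otherwise deaths collected later for overall survival would count as competing events while skeletal events in the interval were missed, which would bias the incidence downward.
3. If a median is wanted, add skeletal-event-free survival (skeletal event or death) by Kaplan-Meier over the same window.

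The cost is a few sentences and standard software. Death dates are already needed for radiographic progression-free and overall survival, but the last date of skeletal ascertainment must be recorded for each patient. Results beyond about 90 days after treatment would need skeletal events to be followed for longer than the calendars now schedule. The downside is that a cumulative-incidence median may not be reached.
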